Summary of Significance: There is a high burden of ESRD in the US and most patients undergo time-intensive HD treatment during which interventions could be administered. Replacing passive intradialytic activities with cognitively beneficial activities is a missed opportunity. CT and ET are the only two effective non-pharmacological interventions to preserve executive function, which is supported by our pilot data. The findings from this RCT will provide nephrologists who care for the vulnerable population of HD patients with the first feasible and effective interventions for their patients who are at risk for experiencing executive function decline. Interventions are needed to target the prevention of executive function decline, rather than simply attempting to reverse decline or regain executive function.

Study Procedures

This is a 2 by 2 factorial randomized controlled trial (RCT). We will randomize participants to CT alone, ET alone, both CT+ET, or SC resulting in four arms. Randomization will be achieved through balancing methods over the three stratification factors: study center, sex, and race/ethnicity.

Study Population: Men and women with ESRD and receiving maintenance HD 2-3 times weekly at one of the 13 hemodialysis centers participating in the trial will be eligible. We will only enroll new HD patients, as has been done in other RCTs (89-91) of HD patients. The rationale for enrolling new HD patients are: 1) they will not have already experienced the executive function decline associated with HD; 2) there is a high dementia incidence even within the first year of HD; 3) survival bias is present when studying prevalent HD patients; and 4) we want to intervene before the neurodegenerative process begins.

Inclusion Criteria:

Participants must be:

- Within 3 months to 3 years of initiating HD
- 18 years or older at enrollment
- English-speaking

- Willing to participate in research

Exclusion Criteria:

Patients with the following conditions will not be included in the study:

- Pregnancy
- Angina pectoris
- Chronic lung disease requiring oxygen
- Musculoskeletal conditions that limit mobility
- Upper or lower extremity amputation
- Orthopedic disorders exacerbated by physical activity
- Femoral arteriovenous (AV) access
- Blindness/ Legal blindness
- Hepatitis B infection
- Inability to recognize letters and numbers

In addition to patients with these conditions, patients who are currently incarcerated will be excluded from the study.

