Data will be analyzed according to the intention-to-treat principle. We will test the main effect of CT alone (arm 1) and the main effect of ET alone (arm 2) as well as the interaction between CT+ET (arm 3) compared with SC (arm 4). Baseline characteristics will be compared among treatment groups to test adequacy of randomization and identify possible confounders. If there are concerns about imbalances between treatment groups with respect to important risk factors for executive function decline, we will adjust regression-based models as necessary to account for these differences. Competing events (death or KT) will be quantified; if relevant, sensitivity analysis accounting for competing events will be performed.

1.0. Analytic Methods. Effect of CT, ET, and CT+ET on cognitive outcomes:

Change in executive function between baseline and 3 months will be a continuous outcome. Using a linear regression with the cluster option to account for the centers, we will test the null hypothesis (H01) of no difference in the mean change in executive function in CT alone vs. SC against the alternative hypotheses (HA1) that CT alone has a different mean change in executive function than SC. We will then test the null hypothesis (H02) of no difference in the mean change in executive function in ET vs. SC against the alternative hypotheses (HA2) that ET has a different mean change in executive function than SC.

In addition to these two main effects, we will test the effect of CT depends on ET (interaction). The null hypothesis (H03) is that there is no difference in the mean change in executive function for those in the CT, ET, CT+ET or SC arms vs. the alternative hypothesis (HA3) that at least one of the mean changes in executive function differs.

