H05 Not rejected	Arms 1 and 3 are superior to arm 4, but there is not sufficient evidence to distinguish arm 1 from arm 3; i.e., CT+ET is an effective strategy compared with SC, but we cannot tell if the CT+ET is effective beyond that of CT alone.	There is insufficient evidence to distinguish arm 3 from arm 4 and arm 1 from arm 3; i.e., CT+ET is not an effective strategy compared with SC and no better than CT alone.
H06 Rejected	Arm 2 is superior to arm 4 and arm 3 is superior to arm 2; i.e., both CT+ET and ET alone are effective strategies compared with SC but CT+ET is more effective.	Arm 3 is superior to arm 2, but there is not sufficient evidence to distinguish arm 3 from arm 4; i.e., CT+ET is not effective compared with SC but better than ET alone.
H06	Arms 1 and 3 are superior to arm 4, but there is not sufficient evidence to distinguish arm 1 from arm 3;	There is insufficient evidence to distinguish arm 3 from arm 4 and arm 2 from arm 3; i.e., CT+ET is not an effective

Not rejected	i.e., CT+ET is an effective strategy compared with SC, but we cannot tell if CT+ET is effective beyond CT alone.	strategy compared with SC and no better than ET alone.
--------------	--	--

Power Calculations: We used a Monte-Carlo simulation (1,000 randomly generated datasets) to estimate the power of a 2-by-2 factorial design with linear regression and Huber-White robust standard errors. We powered the RCT to detect a statistically significant difference in the CT+ET group based on a 3-month change in executive function, given the group mean change and SD in the pilot data.

When each arm of the study has 47 participants, we will have 80% power to detect a statistically significant change of 20 seconds between baseline and 3 months comparing the CT+ET arm to the SC arm. We will also have 95% power to detect a statistically significant change of 15 seconds in the CT arm and >99% to detect a statistically significant change of 18 seconds in the ET arm. Therefore, we would need to recruit 200 participants from 16 centers (approximately 13 participants per center). Even if we were to recruit just 22 participants (rather than 47) into each arm of the study, we would still have >80% power to observe statistically significant changes of 15 seconds for the main effects of CT and ET.

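### The 80% power for CT+ET vs SC is described for Huber-White errors while section 1.0 tests with errors clustered by centre; if the simulation was unclustered, power for the planned test is about 73–75% when centres do not differ

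*Combined protocol and SAP*

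**What the plan says.** **Power Calculations (protocol, Statistical Methods).** A Monte Carlo simulation of 1,000 datasets was used to "estimate the power of a 2-by-2 factorial design with linear regression and Huber-White robust standard errors", with inputs "given the group mean change and SD in the pilot data". The values of that mean change and SD are not printed. The result is given for the case "When each arm of the study has 47 participants": 80% power is claimed to "detect a statistically significant change of 20 seconds between baseline and 3 months" for CT+ET against SC. Centres appear only afterwards, as a recruitment target: "we would need to recruit 200 participants from 16 centers (approximately 13 participants per center").

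**Section 1.0, Analytic Methods.** The primary test is described differently: "Using a linear regression with the cluster option to account for the centers".

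**Randomization.** Individuals are randomised in blocks of four, stratified by sex, race/ethnicity and dialysis centre, so every arm is represented within centres.

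**Statistical methods update (end of the combined document).** The Statistical Analysis section describes linear regression and an ANCOVA. The main comparison is adjusted for age, education and the baseline value, at two-sided 0.05, in Stata. It mentions neither a cluster option nor a centre term.

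**Number of centres.** Study Population has "receiving maintenance HD 2-3 times weekly at one of the 13 hemodialysis centers participating in the trial will be eligible". The power text has 16. Eligibility in the update has 14 in the Baltimore area plus 1 in New York, which makes 15. The recruitment section names 10 + 4 + 4 = 18 sites.

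**The concern.** A power figure belongs to a particular test. Huber-White errors at the level of the individual use about 184 residual degrees of freedom (188 participants less four arm means). The cluster option estimates the variance from centre totals, and Stata, the package named in the update, refers the statistic to t with (centres − 1) degrees of freedom: 12 for 13 centres, 15 for 16. The critical value rises from about 1.97 to between 2.13 and 2.18.

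The 80% for CT+ET vs SC is the figure that the 47 evaluable (50 recruited) per arm rests on. If it was computed for the unclustered test, the planned test falls short of it at the same sample size. The three descriptions of the analysis also leave it open which standard error is primary, and near the threshold that choice can decide whether the result is called significant.

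**Working it through.** **Inputs from the documents.** Effect 20 s; 47 per arm (50 × 0.94 = 47, using the 6% attrition); stated power 80%; two-sided alpha 0.05 (stated only in the update); 13, 15 or 16 centres.

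**Assumptions.** Equal variance across arms; an unclustered simulation; Stata's reference distribution for the cluster option. No SD or ICC is printed.

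**Step 1: the plan's own figure.** Without an SD, the 80% cannot be reproduced forward. It can be inverted. For a two-sided t test with 184 df, 80% power needs a noncentrality of 2.816. Since noncentrality = 20 / (SD × √(2/47)), the implied standard error is 20/2.816 = 7.10 s and the implied SD is 34.4 s (34.6 s with a normal approximation). This SD is back-solved, not a figure from the documents.

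**Step 2: the same noncentrality at the clustered degrees of freedom.** Power = P(|T| > t₀.₉₇₅,df), with T noncentral t at 2.816.

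| Centres | df | Critical value | Power | Per arm needed for 80% |
|---|---|---|---|---|
| unclustered | 184 | 1.973 | 80.0% | 47 |
| 16 | 15 | 2.131 | 74.9% | 53.3 |
| 15 | 14 | 2.145 | 74.5% | 53.8 |
| 13 | 12 | 2.179 | 73.4% | 55.2 |

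Starting from the normal approximation lowers these to 74.5%, 74.1% and 73.0%. This step needs only the stated 80%; under equal variances, any pairing of SD and effect that yields 80% gives the same answer.

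**Step 3: simulation of the planned test.** 188 participants, four arms, blocks of four within centre by four assumed sex/race strata, equal centre sizes, SD 34.4 s, effect 20 s in CT+ET only, 6,000 datasets per row (Monte Carlo margin about ±1 point).

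| Centres | Assumed ICC | Huber-White | Cluster option | Centre indicators + Huber-White |
|---|---|---|---|---|
| 13 | 0 | 80.4% | 74.0% | 80.1% |
| 13 | 0.05 | 80.6% | 75.0% | 81.7% |
| 13 | 0.10 | 81.2% | 75.9% | 83.1% |
| 16 | 0 | 80.0% | 74.8% | 78.9% |
| 16 | 0.05 | 80.2% | 76.1% | 81.0% |
| 16 | 0.10 | 80.6% | 77.8% | 83.1% |

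Repeat runs that included 15 centres and unequal centre sizes put the cluster option between about 74% and 80% at ICC 0.05–0.10. At ICC 0.20 it returns to about 80%. Arms are balanced within centres, so a common centre effect does not inflate the contrast; a larger ICC makes it more precise. The loss at ICC 0 comes from the critical value and the few centre totals behind the variance, not from a design effect.

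**Step 4: treatment effects that vary between centres.** With an assumed between-centre SD of the CT+ET effect of 0.2–0.3 of the outcome SD and ICC 0.05, power with the cluster option is about 68–73%. Under a zero average effect at 0.3, rejection rates were:

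| Centres | Cluster option | Huber-White | Centre indicators + Huber-White |
|---|---|---|---|
| 13 | 4.8% | 6.2% | 6.7% |
| 16 | 4.8% | 6.0% | 6.3% |

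With a common treatment effect and equal centre sizes, the cluster option and plain Huber-White errors were both near 5%. With unequal centre sizes the cluster option ran at about 5.5–6.4%.

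**Step 5: the trial as run.** 121/4 is about 30 per arm. At the back-solved SD, power for 20 s is about 61% before any clustering.

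**The case against.** *The simulation may have been clustered.* Cluster-robust errors are an extension of Huber-White errors, and the same paragraph plans 16 centres of about 13. This stands as a limit: an unclustered simulation is an inference. It remains the natural reading, because section 1.0 names the cluster option where clustering is meant and the power text gives no ICC.

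*The later methods supersede section 1.0.* The update mentions no clustering and adjusts for covariates. An R² of about 12–15% (residual SD from 34.4 to about 32.3 s at 15 df or 31.8 s at 12 df) would bring the clustered test back to 80%. This is fair. But the update neither withdraws nor confirms the cluster option, and no stated power takes account of the covariates.

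*The implied SD does not fit the other power claims.* At a common SD of about 34.6 s, even marginal main effects give 84% for 15 s (95% stated), 95% for 18 s (more than 99% stated) and 53% for 15 s at 22 per arm (more than 80% stated). So equal variance may not describe the sponsor's simulation. Step 2 does not use the SD, but it does assume equal variances.

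*Clustering is pointless under individual randomisation.* A reader might infer this from Step 3. Step 4 does not support it: the interventions are delivered and supervised on site, effects that differ by centre are plausible, and there the cluster option holds its level better than the alternatives.

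**Conclusion.** The mismatch between the power text and section 1.0 is on the page, and the updated methods leave it unresolved. On the natural reading, the planned test has about 73–75% power at 47 per arm with 13–16 centres and ICC 0, a loss of 5–7 points. At ICC 0.05–0.10 it has about 75–80%, and if treatment effects vary by centre it has less, about 68–73% in the settings tried. These figures rest on an unclustered simulation, equal variances and the t reference with (centres − 1) df.

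A reader might infer that the trial simply has 73–75% power. The documents do not support that: it is the ICC 0 result under an inference about the simulation, and 47 per arm was never reached. At 121 randomised, the smaller sample costs far more power than the choice of standard error. What is at stake is whether the stated power is valid for the stated test, and which critical value decides the primary comparison.

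**What to change.** Name one primary standard error, and use it consistently in section 1.0, the Power Calculations and the updated Statistical Analysis. Reconcile the centre count (13, 16 or 15), since under the cluster option it sets the degrees of freedom.

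- **If the cluster option is kept:** rerun the simulation with it and restate the CT+ET vs SC power (about 73–75% at ICC 0), printing the SD, ICC, centre count and reference distribution. If the existing simulation was already clustered, saying so and printing those inputs is enough.
- **If it is not kept:** use individual-level Huber-White errors with centre, already a randomisation factor, entered as indicators, and report the cluster-option result as a sensitivity analysis. The downsides are small: about 1 point of power if centres do not differ, and a type I error of about 6–7% if treatment effects vary by centre to the degree assumed in Step 4.

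The cost is a sentence or two and one restated power figure, with no extra patients or data. It cannot recover the planned power, so any report should describe the 80% as the design target at 47 per arm and not as the power of the 121 randomised.

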CT and ET are the only two effective non-pharmacological interventions to impact executive function in older adults. CT+ET over 3 months improved executive function (29, 45, 50, 59) and is more effective than either CT or ET alone (31, 50). CT+ET enhances synaptic connections between brain cells and improves brain plasticity (60, 61). To our knowledge, no studies have tested whether CT+ET impacts executive function among HD patients.

Although all intervention studies designed to preserve executive function have been conducted in older adults, this population has a very different physiology and distinct risk factors for executive function decline. Therefore, these interventions must be tested in HD patients to draw appropriate inferences about their safety and effectiveness.

[figure not shown]
Our pilot RCT of 20 HD patients suggests that intradialytic CT and ET prevent the profound decline in executive function. After 3 months, participants in the intradialytic CT (Lumosity® on a tablet) and ET (foot peddlers) arms had less decline in executive function than those with standard of care (SC), based on the Trail Making Test (TMTA and TMTB) times (Figure) ([name], Under Review J Neph). Strikingly, the improvement in TMTB was nearly a minute greater for those in the CT (difference= 47 seconds; P=0.03) and ET arms (difference= 56 seconds; P=0.03), compared with those in the standard of care arm.

Our pilot study of physicians (n=41, 87% response rate) found that 57% believed their ESRD patients could improve cognitive function through intradialytic CT, such as playing tablet-based brain games, and 83% agreed that intradialytic ET, such as using a foot peddler, would improve physical function. They believed their patients would be interested in these interventions (CT: 87%; ET: 83%) and the logistics would be feasible in a dialysis clinic (CT: 93%; ET: 80%). Among HD patients (n=91, 97% response rate), 67% wanted to improve their cognition through intradialytic CT, and 71% wanted to improve their strength and cognition through intradialytic ET.

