Follow-up Assessments: We will perform follow-up assessments at 3 months of intervention and 6 months of intervention (measures listed in Table 2) in the dialysis center using a similar approach to the baseline assessment for comparability of the measures. Research assistants blinded to the assigned study arm will perform follow up assessments.

The Principal Investigator/ Program Manager will inform the appropriate dialysis center treating nephrologist/nurse practitioner of any abnormal findings for cognitive function, anxiety, and depression at the 3 month and 6 month assessments.

Data collection for variables needed for DSMB review. Falls during the intervention or assessment will be directly observed by study staff at each intervention session throughout the whole study. Hypotension (SBP<110 mmHg or DBP<50 mmHg) and hypertension (SBP>150 mmHg or DBP>90 mmHg) will be identified during the clinical measurements of blood pressure that occur approximately 10 times throughout the dialysis session. Similarly elevated heart rate (>80% of maximum heart rate calculated as 220-participant age will be identified during the clinical measurements of heart rate that occur approximately 10 times throughout the dialysis session. Cramping and headaches will be noted if a participant tells the study staff that they are experiencing these events. Injurious falls for DSMB review outside of the dialysis session will be self-reported by participants as part of the questionnaire at 3- and 6-months follow-up.

Plan for Fidelity Monitoring. In the pilot study, there was a small dropout rate (3/23), which is consistent with other intradialytic exercise interventions at 6 months (86) and there is high compliance (88%) with ET (63). We will allow for temporary noncompliance due to acute illness or travel. We will add additional sessions onto the end of the intervention period (no more than 2 weeks) in any of the study arms, as has previously been proposed in intradialytic intervention trials (86). The Program Manager/Study Coordinator

will visit the dialysis centers administering these arms of the study monthly throughout the course of the intervention to give a refresher on the safe and effective use of the foot peddlers. The PI or project manager will visit each clinic weekly during the administration of the intervention to directly observe compliance and facilitate communication among the HD clinic staff, patients, and study staff. Research assistants will record the:

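### The stated 95% (CT, 15 s) and >99% (ET, 18 s) power does not hold for TMTB under the planned pairwise tests if the SD is what the pilot's TMTB results imply; test, SD and contrast are not stated

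*Combined protocol and SAP*

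**What the plan says.** The primary outcome is the 3-month change in executive function, measured by TMTA and TMTB. In section 1.0 (Analytic Methods), H01 compares CT alone with SC and H02 compares ET with SC.

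The Power Calculations paragraph describes a simulation of the 2-by-2 design with robust standard errors, run "given the group mean change and SD in the pilot data". It continues: "We powered the RCT to detect a statistically significant difference in the CT+ET group based on a 3-month change in executive function". At 47 per arm it gives 80% for 20 s (CT+ET against SC). For CT it says: "We will also have 95% power to detect a statistically significant change of 15 seconds in the CT arm". For ET it gives more than 99% for 18 s. No SD is printed, and the paragraph does not say whether the seconds are TMTA or TMTB.

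The pilot is described under Background and Significance: "Our pilot RCT of 20 HD patients suggests that intradialytic CT and ET prevent the profound decline in executive function". The only outcome with numbers there is TMTB, where the improvement over SC is given "for those in the CT (difference= 47 seconds; P=0.03) and ET arms (difference= 56 seconds; P=0.03". The text describes CT, ET and SC arms. Arm sizes, SDs and the test used are not given.

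**The concern.** The plan names the pilot as the source of its SD, so the pilot's reported results are a fair check on the power figures. A difference, a P value and an approximate arm size together fix an SD. If that SD is well above what 95% and >99% require, those figures do not describe the TMTB comparison.

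The stake is how a null result is read. With 95% to >99% design power behind it, a null TMTB finding would count as good evidence against effects of 15-18 s. With power nearer one half, it would not. There is also a question of source: the headline 80% is for CT+ET and is attributed to pilot data, but the pilot text describes no CT+ET arm.

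**Working it through.** **Inputs.** 47 per arm; 15, 18 and 20 s; 95%, >99% and 80% (Power Calculations). Two-sided 0.05 (Statistical Analysis in the later update). Pilot: 20 patients, 47 s and 56 s, each P=0.03 (Background and Significance). Assumed: 6-7 patients per pilot arm, and an unadjusted t-test on mean change.

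**Step 1. Reproducing the stated power.** This cannot be done directly because no SD is given. Solving instead for the SD that each figure needs, pairwise:

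SD = difference / [(1.96 + z_power) × √(2/47)], with √(2/47) = 0.2063.

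- CT: 15 / (3.605 × 0.2063) = 20.2 s
- ET: 18 / (4.286 × 0.2063) = 20.4 s at most
- CT+ET: 20 / (2.802 × 0.2063) = 34.6 s

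On factorial margins (94 vs 94, √(2/94) = 0.1459) the CT and ET figures need 28.5 s and at most 28.8 s. Reading the CT or ET figure as a change within one arm of 47 gives the same values, since √(1/47) = √(2/94).

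**Step 2. SD implied by the pilot TMTB results.** SD = difference / [t × √(1/n₁ + 1/n₂)], with t the two-sided P=0.03 point.

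| Pilot arms | t (two-sample) | CT, 47 s | ET, 56 s | CT, pooled 17 df (t = 2.368) | ET, pooled 17 df |
|---|---|---|---|---|---|
| 6 / 6 | 2.527 | 32.2 | 38.4 | 34.4 | 41.0 |
| 7 / 6 | 2.491 | 33.9 | 40.4 | 35.7 | 42.5 |
| 7 / 7 | 2.461 | 35.7 | 42.6 | 37.1 | 44.2 |
| 5 / 5 | 2.634 | 28.2 | 33.6 | 31.4 | 37.4 |

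With 6-7 per arm the SD is about 32-37 s for CT vs SC and 38-44 s for ET vs SC. Approximate 95% limits (two-sample t, 6-7 per arm) are 23-59 s and 27-70 s.

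**Step 3. Power at 47 per arm.** Power = Φ[difference / (SD × √(2/n)) − 1.96].

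| Comparison | Stated | Pairwise, SD 35 | Pairwise, SD 42 | Margin, SD 35 | Margin, SD 42 |
|---|---|---|---|---|---|
| CT, 15 s | 95% | 55% | 41% | 84% | 69% |
| ET, 18 s | >99% | 70% | 55% | 94% | 84% |

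Taking each contrast at its own central SD (35 s for CT, 42 s for ET) gives 55% for each pairwise and 84% for each on the margin.

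**Step 4. Comparison within the same paragraph.** At the 34.6 s needed for the stated CT+ET figure, read pairwise with a common SD, CT at 15 s has 56% and ET at 18 s has 71%.

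**Step 5. Detectable difference at 80%, pairwise.** 2.802 × 0.2063 × 35 = 20.2 s; with SD 42, 24.3 s.

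**The case against.** The power paragraph never says that its figures are for TMTB. Its effects of 15-20 s are far below the pilot TMTB differences, and the pilot also measured TMTA, for which no SD is given. The figures may be right for TMTA. This stands, but it would leave TMTB, one of the two primary scores, without stated power.

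The pilot SD is reconstructed from a rounded P value, assumed arm sizes and an assumed test, and it is imprecise. This also stands, and it matters most on the margin. With 5 patients in each of the CT and SC pilot arms, the SD is 28.2 s and the margin gives 95% for CT, as stated. That split would follow if the other 10 patients were all in the ET arm, or if the pilot had four equal arms. The same split does not rescue ET: at 33.6 s the margin gives 96%. The margin reading is not far-fetched, because the simulation is of a factorial design and the paragraph's last sentence speaks of main effects. H01 and H02, however, are written pairwise. The roughly 20 s needed there lies below the lower 95% limits with 6-7 per arm. With 5 per arm the lower limit for CT falls to 19 s.

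Step 4 assumes a common SD. The plan refers to group SDs, so a more variable CT+ET arm could reconcile the figures: with 20.2 s in SC, it would need √(2 × 34.6² − 20.2²) = 44.6 s. That is an unstated input.

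Finally, the trial ended with 121 randomized, and the updated models adjust for age, education and baseline outcome. The 47-per-arm figures therefore no longer describe the analysis performed. They remain the only power statement in the documents.

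**Conclusion.** The stated CT and ET power does not hold for TMTB under the planned pairwise tests if the SD is what the pilot results imply. At 35-42 s, power is about 41-55% for CT (stated 95%) and 55-70% for ET (stated >99%). On factorial margins the shortfall is smaller, at 69-84% and 84-94%, and it disappears for CT in the 5-per-arm case. The conclusion rests on near-equal pilot arms of 6-7 and an unadjusted t-test.

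A reader might infer that the simulation was run wrongly, that the figures cannot be for TMTB, or that the true power is about 55%. The documents support none of these: test, contrast and SD are unstated, and the SD used here is a back-calculation. Nor is the headline 80% for 20 s contradicted, since its implied pairwise SD of 34.6 s fits the low end of the TMTB range.

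It also does not follow that the pilot lacked a CT+ET arm. The text describes none, but the pilot figure is not available here. What can be said is that the source of the CT+ET inputs is not shown.

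**What to change.** Re-run the simulation with the actual pilot SDs, separately for TMTA and TMTB, for the contrasts in H01 and H02. Replace 95% and >99% with the resulting values, or with the detectable difference (for TMTB, about 20-24 s at 80% power if the SD is 35-42 s). The replacement should come from the sponsor's pilot data and not from the back-calculated percentages above. State the test, the SD per arm and the contrast behind each power figure. Label the CT+ET effect and SD as assumptions unless the pilot had such an arm, and in that case say so.

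The cost is one re-run of an existing simulation and a rewritten paragraph. The TMTB figures will probably look less favourable.

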From this model, we will use linear combination methods to test H04 (no difference in mean change in executive function for arm 1 vs. 2) vs. HA4 (arm 1 has a different mean change in executive function than arm 2). We will then test H05 (no difference in mean change in executive function for arm 1 vs. 3) vs. HA5 (arm 1 has a different mean change in executive function than arm 3). We will test H06 (no difference in mean change in executive function for arm 2 vs. 3) vs. HA6 (arm 2 has a different mean change in executive function than arm 3). If H01 is not rejected, we will conclude that there is insufficient evidence that arm 1 is more effective than arm 4 in preserving executive function. If H02 is not rejected, we will conclude that there is insufficient evidence that arm 2 is more effective than arm 4 in preserving executive function. If H03 is not rejected, we will conclude that there is insufficient evidence that arm 3 is more effective than arm 4.

If H01, H02, and H03 are rejected, but H04 is not rejected, we will conclude that arms 1 and 2 are more effective than arm 4, but there is no difference in the effectiveness of arms 1 and 2. Similarly, if H01, H02, and H03 are rejected, but H05 is not rejected, we will conclude that arms 1 and 3 are more effective than arm 4, but there is no difference in the effectiveness of arms 1 and 3. And finally, if H01, H02, and H03 are rejected, but H06 is not rejected, we will conclude that arms 2 and 3 are more effective than arm 4, but there is no difference in the effectiveness of arms 2 and 3. The following table below details the conclusions we will draw based on hypotheses testing if H01 and H02 are rejected:

Table 3: Hypothesis Testing for the Primary Outcome

Table 3: Hypothesis Testing for the Primary Outcome		
	H03 rejected	H03 not rejected
H05 Rejected	Arm 1 is superior to arm 4 and arm 3 is superior to arm 1; i.e., both CT+ET and CT alone are effective strategies compared with SC but CT+ET is more effective.	Arm 3 is superior to arm 1, but there is not sufficient evidence to distinguish arm 3 from arm 4; i.e., CT+ET is not effective compared with SC but better than CT alone.

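### The two CT power figures for 15 s (95% at 47 per arm, above 80% at 22 per arm) cannot both be power for H01, CT alone versus standard of care

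*Combined protocol and SAP*

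**What the plan says.** All the power figures stand in the protocol's Power Calculations paragraph, under Statistical Methods, section 1.0. They come from 1,000 simulated datasets of a 2-by-2 factorial design, analysed by linear regression with robust standard errors, "given the group mean change and SD in the pilot data". No SD is printed.

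At 47 per arm the paragraph claims:
- "80% power to detect a statistically significant change of 20 seconds between baseline and 3 months comparing the CT+ET arm to the SC arm";
- "95% power to detect a statistically significant change of 15 seconds in the CT arm";
- more than 99% for 18 s in the ET arm.

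The fallback sentence follows: "Even if we were to recruit just 22 participants (rather than 47) into each arm of the study, we would still have >80% power" for 15 s, described as the main effects of CT and ET.

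The same part of the protocol says what a main effect is. The opening of Statistical Methods says "We will test the main effect of CT alone (arm 1) and the main effect of ET alone (arm 2"). Section 1.0 states H01 as "no difference in the mean change in executive function in CT alone vs. SC" and H02 likewise for ET, then continues: "In addition to these two main effects, we will test the effect of CT depends on ET (interaction"). The conclusions hang on these tests: "If H01 is not rejected, we will conclude that there is insufficient evidence that arm 1 is more effective than arm 4". The SAP's Statistical Analysis section still speaks of main effects of CT alone and ET alone.

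**The concern.** The effect (15 s) and, on the plan's own terminology, the test (H01) are the same in the two sentences. Only the number per arm differs, 47 against 22. Cutting the sample by more than half should cost more power than a fall from 95% to something above 80%.

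The fallback sentence is the only power statement in the documents for a reduced sample, and a reduced sample is what occurred: the SAP reports 121 randomised, about 30 per arm (121/4 = 30.25), with 25 three-month follow-ups interrupted. A reader who takes the sentence as power for H01 and H02 would give a null result on those tests more weight than the 95% figure supports.

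**Working it through.** **Inputs.** Difference 15 s, 95% at 47 per arm, above 80% at 22 per arm, more than 99% for 18 s (ET) at 47, and 80% for 20 s (CT+ET) at 47, all from Power Calculations. Equal allocation, from Randomization. Two-sided 5%, stated only in the SAP's Statistical Analysis section. The arm SDs are not given.

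**Formula.** Power ≈ Φ(δ − 1.960), with δ = difference / √((s₁² + s₄²)/n). For a fixed contrast, outcome and SDs, δ is proportional to √n, so the SDs cancel, even if unequal.

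**1. The 95% figure.** δ at 47 = 1.960 + 1.645 = 3.605. With equal SDs this corresponds to an SD of 20.17 s. The figure can only be back-solved, since no SD is printed.

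**2. Forward, 47 to 22.** δ = 3.605 × √(22/47) = 3.605 × 0.684 = 2.466. Power = Φ(0.506) = 69.4%. For 80%, n = 47 × (2.802/3.605)² = 28.4, so 29 per arm.

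**3. Reverse, 22 to 47.** δ at 22 for 80% = 1.960 + 0.842 = 2.802. At 47, δ = 2.802 × √(47/22) = 4.095. Power = 98.4%, and higher for anything above 80%.

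**4. Sensitivity of the 69.4%.**
- Simulation error: SE = √(0.95 × 0.05/1000) = 0.0069, so 93.6 to 96.4% at 47, which gives 66 to 73% at 22.
- t-based tests 68.3 to 68.8%; simulated robust standard errors 68.8 to 70.7%; one-sided 5% 72.8%; two-sided 2.5% 66.2%.
- If both sentences describe pooled margins, the second is again 69.4%.
- One contrast satisfies both figures only at a two-sided alpha of about 0.37.

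**5. ET.** 80% for 15 s at 22 would need δ = 2.802 × √(47/22) × 18/15 = 4.914 for 18 s at 47, a power of 99.84%. The text says only that power exceeds 99%, so the ET fallback can be right for H02. Power for H02 at 22 is 69% if the bound means 99.0%, 73% if 99.5% and 82% if 99.9%.

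**6. Can all the figures stand?** Yes, if the fallback is the pooled margin (for CT, arms 1+3 versus 2+4), whose SE is √(sum of the four variances/(4n)). Two sets of assumed SDs, in the order CT, ET, CT+ET, SC:

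| Quantity | Stated | 8, 7, 40.5, 27.4 s | 20, 20, 34, 20 s |
|---|---|---|---|
| CT vs SC, 15 s, n = 47 | 95% | 95.0% | 95.3% |
| ET vs SC, 18 s, n = 47 | >99% | 99.2% | 99.2% |
| 20 s, n = 47 | 80% | 80.1% (CT+ET vs SC, as worded) | 80.6% (interaction); 93.5% as worded |
| Pooled CT or ET, 15 s, n = 22 | >80% | 80.3% | 82.6% |
| H01, 15 s, n = 22 | – | 69.3% | 70.1% |

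Keeping the 20 s figure as worded requires very uneven arms: an SC SD of at least 26.2 s with a CT SD of at most 11.3 s. Under either set, H01 at 22 per arm stays at about 69 to 70%.

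**7. At the size reached.** If the 95% is right, unadjusted H01 power for 15 s is 82.1% at 30 analysed per arm, 80.8% at 29 and 79.5% at 28.

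**The case against.** The strongest reply is that no figure has been shown to be wrong. The two sentences use different words (CT arm at 47, main effects at 22), the simulation was of a factorial design, and main effects there usually means margins. With equal SDs of 20.17 s the pooled CT effect at 22 per arm has 93.7% power, so both figures hold. This stands as a possible account of what was simulated. It does not remove the problem, because section 1.0 gives the term main effects to H01 and H02. On that account the label is wrong instead of the number.

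Other conditions also stand. The incompatibility needs the same outcome in both sentences, and the paragraph does not say TMTA or TMTB. It needs 95% to be a point value: read as at least 95%, both figures hold at an SD of about 17.8 s or less. The neighbouring figures are marked as bounds and this one is not, which favours a point value. A centre-level variance that does not shrink with n could reconcile them, but it would have to be about 42% of the variance at 47 per arm, and none is described.

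A reader might go further than the documents allow:
- **That the 20 s figure must be the interaction.** Step 6 shows SDs under which it stands as worded. They are uneven, but no SDs are printed to exclude them.
- **That ET has the same conflict.** Step 5 shows it need not.
- **That the trial was mis-sized, or under-powered as run.** The fallback sentence did not set the sample size and the SAP does not rely on it. The analysed number is not stated. The SAP's main comparison also adjusts for age, education and the baseline measure. If those covariates correlated 0.4 to 0.5 with the change (an assumption), 69% at 22 would become about 77 to 81%. The stated figures are not described as adjusted.

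**Conclusion.** The point holds for CT. At most one of the two 15 s figures can be power for H01: either about 69% belongs where above 80% is printed, or about 98.4% or more where 95% is printed. Otherwise the fallback describes a contrast that section 1.0 does not test as H01. This rests on a common outcome and common SDs at both sizes, two-sided 5%, 95% as a point value, and no variance component that persists as n grows. It does not depend on any particular SD. The documents do not show which figure or label is at fault. The consequence is limited to how the reduced-sample power is read; the planned 47 evaluable per arm is unaffected.

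**What to change.** Identify from the simulation the contrast, the outcome (TMTA or TMTB) and the arm SDs behind each power figure, and print them. Then one of three changes applies:

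1. If 95% at 47 is right for H01, restate H01 power at 22 per arm as about 69%, unadjusted.
2. If above 80% at 22 is right for H01, restate the 95% at 47 as about 98% or more.
3. If pooled margins were simulated, label the 22-per-arm sentence as pooled main effects (arms 1+3 versus 2+4, and 2+3 versus 1+4), say that it is not power for H01 or H02, and give H01 and H02 power at 22 from the same SDs.

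Leave the 20 s figure as worded unless the simulation shows that it was the interaction.

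The cost is checking or re-running a short simulation and editing a few sentences, with no extra participants and no design change. The drawback is that the stated H01 power at 22 per arm may be less favourable.
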